# **10. STATISTICAL CONSIDERATIONS**

## **10.1. Sample Size Determination**

This study is designed to assess the level of receptor engagement as measured by the effect of nebulised GSK3008348 on the  $\alpha\beta6$ -associated PET signal ( $V_T$ ). The PET data from the 5 participants in Cohort 1 receiving GSK3008348 will be used. This sample size has been chosen based on considerations given to: a) the probability of declaring a successful study for reductions in  $\alpha\beta6$ -associated PET signal deemed to be representative of the expected receptor engagement activity, and b) the within-subject variability of the PET signal.

The chosen study success criteria is defined as  $\text{Prob}(\theta < 0 | \text{Study Data, Prior}(\theta)) \geq 80\%$ , where  $\theta$  is the unknown true logarithm of the ratio of  $\alpha\beta6$ -associated PET signal post-dose / pre-dose in patients receiving GSK3008348, and the prior distribution for  $\theta$  is non-informative. Assuming the within-subject standard deviation is as previously observed in study [RES116235](#) (within-subject standard deviation following two PET scans was estimated to be 0.15, 95% CI [0.099, 0.34]), consideration was given to the probability of achieving the study success criteria for a range of true reductions in  $\alpha\beta6$ -associated PET signal with GSK3008348. In addition, the minimum detectable effect (MDE), i.e., the minimum observed reduction in  $\alpha\beta6$ -associated PET signal leading to the success

criteria being achieved, was also derived. In particular, if the true reduction in  $\alpha\beta 6$ -associated PET signal is 14% then there is 86% probability of achieving the above success criteria, and the MDE is a 6.2% reduction in  $\alpha\beta 6$ -associated PET signal.

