## 10.3. Statistical Analyses

### 10.3.1. Pharmacodynamic Analyses

Endpoint	Statistical Analysis Methods
Volume of distribution [ $V_T$ ] in whole lung, not corrected for air volume	The logarithm of the $\alpha\beta 6$ -associated PET signal as measured by $V_T$ will be analysed assuming that it follows a normal distribution. The mean or median signal level pre- and post-dose, as appropriate depending on the posterior distribution, along with the median difference post-dose – pre-dose, will be estimated and the corresponding 95% credible intervals will be produced. The posterior probability that the true difference in the logarithm of $\alpha\beta 6$ -associated PET signal post-dose vs pre-dose is less than 0 will be calculated. Non-informative priors will be used for all the parameters in the statistical model.
Secondary	Will be described in the reporting and analysis plan (RAP)
Exploratory	Will be described in the RAP

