12.2.1.1. Prior Distributions

Unless otherwise specified, the following will be the default approach to selecting prior distributions:

- Non-informative priors of the form Normal (0, Var=1E6) will be assigned to each fixed-effect parameter in the proposed statistical model.
- For repeated measures models, non-informative Inverse-Wishart priors of the form IW (υ, Σ) will be assigned for the Variance-Covariance (VC) matrix associated with the repeated measures timepoints. The parameter υ represents the dimension of VC (number of rows or columns) and the matrix Σ is an identity matrix of the same dimension as VC. The unstructured variance covariance structure for the repeated measurements will be assumed. In cases of non-convergence, the Toeplitz structure will be used.
 - o If there are issues with these distribution parameters, then Σ may be a diagonal matrix that uses best guesses for the residual variance at each repeated measure timepoint (or the residual estimate from fitting simple models). This only needs to be of the correct order of magnitude.
- Non-informative inverse-gamma priors of the form IG(a=2.001, b=0.001) will be used for scale parameters (variances). If these parameters do not lead to convergence, then choose "a" small and "b" smaller than the expected standard deviation.

It is good practice to ensure that each prior distribution is visualized to ensure it appears sensible, i.e., that it allows parameter values that generate clinically plausible response values and that it is truly non-informative over the region of the likelihood function where the data lies.

Note:

• The Gamma(a,b) density function takes the form

$$p(u) = \frac{b(bu)^{a-1}e^{-bu}}{\Gamma(a)}, u > 0$$

The mean is a/b and the variance is a/b^2 .

• The IG(a,b) density function takes the form

$$p(u) = \frac{b^a u^{-(a+1)} e^{-b/u}}{\Gamma(a)}, u > 0$$

The mode is b/(a+1), the mean is b/(a-1), if a>1, and the variance is $b^2/[(a-1)^2(a-2)]$, if a>2.

• There is no requirement to formally report the prior visualisation outputs.

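### The default variance prior IG(2.001, 0.001) is strongly informative, not non-informative; if a Toeplitz or other scalar-variance fallback took it, the PET1/Pre-dose interval would be about 17–22% too narrow

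*SAP*

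**What the plan says.** Protocol 10.3.1 commits the analysis of log V_T to this: "Non-informative priors will be used for all the parameters in the statistical model". Protocol 10.1 gives the planning variability: "within-subject standard deviation following two PET scans was estimated to be 0.15, 95% CI [0.099, 0.34". It sets success as a posterior probability of at least 80% that the log ratio post-dose/pre-dose is below zero, and it fixes the data: "The PET data from the 5 participants in Cohort 1 receiving GSK3008348 will be used".

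SAP 7.1.5.1 models log V_T at three scans (Pre-dose, PET1, PET2) with an unstructured 3x3 covariance matrix. The secondary, exploratory and interim PD analyses follow the same or a similar specification.

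SAP 12.2.1.1 then gives default priors:
- For repeated-measures covariance matrices, an inverse-Wishart with its parameter equal to the dimension and an identity scale matrix. A diagonal best-guess scale is allowed if there are issues.
- For the fallback structure: "In cases of non-convergence, the Toeplitz structure will be used".
- For scalar variances: "Non-informative inverse-gamma priors of the form IG(a=2.001, b=0.001) will be used for scale parameters (variances". If that does not converge, the SAP advises a small a and a b below the expected standard deviation.
- For the inverse-gamma moments: "The mode is b/(a+1), the mean is b/(a-1), if a>1".

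The same section calls it good practice to view each prior and confirm that it is non-informative where the likelihood lies, but it does not require this to be reported.

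**The concern.** A variance prior is non-informative only if it is diffuse over the values that the data can plausibly support. The protocol states what those values are, and this prior is concentrated well below them. Where it is used, it pulls the variance down. Posterior intervals for the PET ratio then narrow, and the posterior probability that drives the 80% rule moves further from one half.

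With five treated participants, a prior worth about 4 degrees of freedom is not swamped by the data. A change of covariance structure made only for computational reasons could therefore also change the apparent precision, and nobody would have decided that it should.

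The convergence advice adds a second problem. It compares b, which is on the variance scale, with a standard deviation.

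**Working it through.** **1. The plan's own figure.** The protocol reports, for a true reduction of "14% then there is 86% probability of achieving the above success criteria, and the MDE is a 6.2% reduction in" PET signal. Take n = 5, a flat prior, a t posterior with 4 df, and 0.15 as the SD of the log ratio.
- SE = 0.15/√5 = 0.0671.
- Smallest successful reduction = 1 − exp(−0.941 × 0.0671) = 6.1%, against 6.2% stated.
- Probability of success with a shifted central t: T4(0.1508/0.0671 − 0.941) = 86.9%, against 86% stated. The exact noncentral t gives 90.3%.

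The protocol does not give its formula. The match suggests that 0.15 was used as the SD of the log ratio, which implies 0.15/√2 = 0.106 per scan. Both readings are carried below where they matter.

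**2. What IG(2.001, 0.001) says about the SD.**
- Mean variance = 0.001/1.001 = 0.000999, so an SD of 0.032. The planning variance is 0.15² = 0.0225.
- SD quantiles: median 0.024, 95% range 0.013 to 0.064.
- P(SD ≥ 0.099) = 0.48%; P(SD ≥ 0.15) = 0.096%; P(SD ≥ 0.34) = 0.004%.
- Prior weight = 2a = 4.0 df.

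**3. Where it can enter.** An unstructured 3x3 matrix with an inverse-Wishart prior leaves no separate scalar variance for it. A Toeplitz matrix is not a general covariance matrix, so that inverse-Wishart prior cannot be placed on it directly. A Toeplitz matrix also has a common variance, and the SAP's only default for a scalar variance is this inverse-gamma. That the fallback would take it is an inference; the SAP does not say.

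**4. Size if it is used.** In each case the means have flat priors and the data are complete.

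*(a) Common residual variance, 15 scans.* Residual df = 15 − 5 − 3 + 1 = 8, with SD 0.15 per scan.
- Reference half-width: 2.306 × 0.15 × √(2/5) = 0.219.
- With the prior: shape 2.001 + 4 = 6.001; scale 0.001 + 8 × 0.0225/2 = 0.091; SE = √(2 × 0.091/6.001/5) = 0.0779; df = 12.0; half-width 2.179 × 0.0779 = 0.170.
- Ratio 0.78, which is 22% narrower. In simulation, coverage is 89% and success under no effect is 25%, against 95% and 20%.

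*(b) Homogeneous Toeplitz, 5 participants by 3 scans.* Uniform prior on admissible correlations, per-scan SD 0.106 or 0.15, between-participant SD 0.1 to 0.3, compared with IG(0.001, 0.001).
- Half-width ratio 0.81–0.83, which is 17–19% narrower. The threshold for the 80% rule falls by 13–16%.
- With this correlation prior the reference interval is itself conservative. Coverage therefore stayed close to or above 95%, and success under no effect stayed near or below 20%. The narrowing here is relative to the diffuse-prior interval.

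*(c) Single variance on five paired log ratios, SD 0.15.* The SAP does not specify this model.
- Reference half-width: 2.776 × 0.0671 = 0.186.
- With the prior: df = 8.0; SE = √((0.001 + 2 × 0.0225)/4.001/5) = 0.0480; half-width 0.111.
- Ratio 0.59, which is 41% narrower. Coverage is 83% and success under no effect is 28%. The smallest successful reduction falls from 6.1% to 4.2%.

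**5. The convergence advice.** A b just under 0.15 satisfies the sentence, yet it is 0.15/0.0225 = 6.7 times the planning variance.

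**The case against.** The strongest objection is that the planned analysis does not touch this prior. The primary, secondary, exploratory and interim PD intervals come from the unstructured model with the inverse-Wishart prior. This stands. A reader might infer that the trial's intervals are about 40% too narrow, and the documents do not support that. The 40% belongs to case (c), and under the specified prior the direction is the opposite. With an inverse-Wishart on 3 df and an identity scale, taken literally, the PET1/Pre-dose posterior is a t with 5 df. Its SE is √((2 + 4 × 0.0225)/5/5) = 0.289 and its half-width is 0.743, about 4 times the reference 0.186. That is a separate matter, and replacing the inverse-gamma prior does not address it.

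It is also tempting to say that five participants make the fallback likely. The documents do not support that either. The inverse-Wishart prior is proper and conditionally conjugate, SAP 12.2.1.3 asks programmers to exploit conjugacy, and a rescaled diagonal matrix is offered if there are issues. The interim was run with this model, and no switch to Toeplitz is recorded.

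The section is described as guidance, and both the prior check and the comparison with a linear mixed model could expose the problem. This stands only in part. Unreported good practice does not replace a stated default that is wrong.

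Finally, the prior looks diffuse by its variance: 0.001²/(1.001² × 0.001) = 0.001, an SD of 0.032 around a mean of 0.001. That spread comes from a long tail with almost no mass. Only 0.48% of the prior reaches even the lower confidence limit of the planning SD.

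**Conclusion.** The point holds in conditional form. IG(2.001, 0.001) is mislabelled: its 95% SD range of 0.013 to 0.064 lies below the whole confidence interval of the planning SD, it carries about 4 df, and it contradicts protocol 10.3.1.

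It has no effect on the primary model as specified. If a scalar-variance fallback took it, the 95% interval for PET1/Pre-dose would be about 17–22% narrower than under a diffuse variance prior, and the 80% rule would be easier to pass.

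This rests on five participants with three complete scans, flat priors on the means, no covariates, a planning SD of about 0.15, and a homogeneous Toeplitz or common-residual parameterisation, which the SAP does not state. Loss of nominal coverage is shown for the common-residual case (89%). For Toeplitz it depends on the correlation prior, which the SAP also leaves open.

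**What to change.** In SAP 12.2.1.1:
- Replace IG(2.001, 0.001) with a prior that is diffuse over SDs of 0.099 to 0.34, for example a half-normal or half-t on each SD with scale 0.5.
- State that any Toeplitz or other scalar-variance fallback uses this prior, and give the prior for its correlations.
- Delete the sentence that compares b with a standard deviation.
- Record the SAP's own prior check against the SD range 0.099 to 0.34.

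The cost is a few lines of SAP text. The amendment predates the final database freeze, so the change can still be made for the final analysis. A re-run is needed only if a scalar-variance model was fitted with the present prior.

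The statistical cost is wider intervals if the fallback is used. Undoing the narrowing means 1/0.83 = 1.20 to 1/0.78 = 1.28 times the width under the present prior. A half-normal with scale 0.5 errs slightly wider still. In case (a) its half-width is 0.235 against the 0.219 reference, from a posterior for the SD σ proportional to σ^−8 × exp(−0.18/(2σ²)) times the half-normal density, where 0.18 = 8 × 0.0225. Nothing changes for the unstructured model.

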12.2.1.2. Initial Values

The two MCMC chains should be generated using over-dispersed initial values. To achieve this the sample standard deviation of the change from baseline in log(response), SD_hat , should be estimated. The two over-dispersed initial values for the parameters (ResponsebyVisit) should then be sampled from the following normal distribution $N(0, SD = 10*SD_hat)$.

For the remaining model parameters over-dispersed initial values may be drawn at random from their respected prior distribution. If convergence of the Markov chain Monte Carlo (MCMC) algorithm is problematic then alternative estimates may be used (for example, these could be based on maximum likelihood estimates).

12.2.1.3. Convergence Diagnostics

To be able to perform Bayesian inference using MCMC simulations the posterior samples for all the parameters in the model need to be obtained from the corresponding target posterior distribution. To ensure that this is the case the following is a list of convergence diagnostics that can be applied for each parameter:

Comparing MCSE vs. posterior standard deviation:

- The Monte Carlo Standard Errors (MCSE) should be compared with the standard deviation of the posterior distribution (SD) to ensure that only a fraction of the posterior variability is due to the simulation, i.e., the ratio MCSE/SD should be as small as possible, typically < 0.01.
- Adequate values for the number of MCMC samples / thinning / number of burn-in samples should be chosen to ensure that the ratio MCSE/SD for all the parameters in the model is < 0.01.
- In addition, if possible, the number of tuning units and maximum number of tuning iterations may be increased to find a better proposal distribution for the model parameters, which in turn may reduce the MCSE/SD ratio.
- Where possible the code should be written to allow the SAS compiler to identify and make use of conjugacy, since this can greatly reduce the corresponding MCSE/SD ratio.
- Models selected with MCSE/SD values > 0.01 would need a brief remark/justification added to the CSR to clarify why it was not possible to reach the target and why it is believed the subsequent model still has utility from an inference perspective.

Gelman & Rubin diagnostics:

- The Gelman & Rubin diagnostic assessment will be used to assess convergence of the multiple chains.
- The Gelman & Rubin diagnostic is based on running multiple Markov chains, say m, each with n draws, with the different chains started at initial values that should be overdispersed relative to the target posterior distribution. Thus, the m chains yield m possible inferences; to answer the question of whether these inferences are similar enough to indicate approximate convergence, Gelman, 1992 suggested comparing these to the inference made by mixing together the m*n draws from all the sequences as follows: the pooled variance across the chains is compared to the overall within-chain variance using a ratio, usually called the potential scale reduction factor, or \hat{R} .
- Values of \hat{R} close to 1 indicate that each of the m sets of n simulated observations is close to the target posterior distribution.
- Although PROC MCMC in SAS does not provide the Gelman & Rubin R, SAS has provided a macro, %gelman, for determining the statistic (note that for this to work at least two MCMC chains need to be generated, which means that PROC MCMC needs to be call as many times as the number of chains, with the different starting values).

Diagnostic plots and visual inspection:

- Trace plots of samples versus the simulation index can be used to assess some aspects of convergence. The centre of the chain should appear stable with very small fluctuations, i.e., the distribution of points should not change as the chain progresses and the posterior mean and variance are relatively constant.
- Autocorrelation plots provide information on how slow or fast the Markov chain converges. If the autocorrelation does not decrease rapidly this means that the chain needs to be run for longer to achieve convergence.
- Examination of correlation structures between relevant posterior parameters should be used to provide information about what potential issues may be and also what corrective action(s) may be worthwhile attempting.

Convergence for all the parameters in the model needs to be verified (apart from subject-specific random effects).

12.2.2. General Considerations for All Analyses

Model assumptions will be applied, but appropriate adjustments may be made based on the data. If there are any departures from the distributional assumptions, alternative models will be explored using appropriate transformed data.

CONFIDENTIAL

204715

Distributional assumptions underlying the model used for analysis will be examined through graphical approaches by assessing the distribution of the residuals against the assumed distribution of the response, and by assessing the distribution of the residuals against the fitted response values.

Outputs of the residual plots as a check of the normality assumptions of the log(response) will be produced.

13. PHARMACOKINETIC / PHARMACODYNAMIC ANALYSES

Pharmacodynamic and PK-time data may be used to derive population PKPD parameters/models using NONMEM or other currently validated software. The timeline for this analysis and reporting will be independent of the analysis described in this RAP. In an event that GSK3008348 is terminated before these analyses are conducted, they will not be reported.

15. APPENDICES

15.1. Appendix 1: Protocol Deviation Management and Definitions for Per Protocol Population

15.1.1. Exclusions from Per Protocol Population

A subject meeting any of the following criteria will be excluded from the Per Protocol population.

Number	Protocol Deviation	Full, Case by Case and Partial Exclusion [1]
01	Inclusion # 2 – Did not have correct diagnosis of definite or probable IPF	Full
02	Inclusion # 4 – Did not have qualifying lung function severity (Subjects who do not have FVC > 50 % predicted and DLCO > 40 % predicted).	Full
03	Exclusion # 7 - Forced expiratory volume in 1 second (FEV1)/forced vital capacity (FVC) ratio < 0.70 at screening (post-bronchodilator).	Full
04	PET scan at 30 mins post-dose non-evaluable	Full
05	Visit outside of protocol defined window	Case by case
06	Exclusion # 4 – Current IPF exacerbation or upper or lower respiratory tract infection on admission to the clinical unit.	Partial
07	Exclusion # 10 - Subjects who are currently taking Pirfenidone or Nintedanib or who have received Pirfenidone or Nintedanib within the 30 days prior to the first dosing day will be excluded from the study.	Partial

NOTES:

^[1] Partial exclusions refer to patients for whom data will be excluded from the Per-Protocol population only from the study day at which the deviation takes place onwards. Full exclusions refer to patients for whom all the available data will be excluded from the Per-Protocol population. Other protocol deviations not listed in this section will be assessed on a case by case basis.

15.2. Appendix 2: Schedule of Activities

15.2.1. Protocol Defined Schedule of Events

	Screening	Dosing period 1		Wash- out period			d 2 u		Comments		
Procedure	Day ≤-30	Day -11	Day 1	Day 2	(7-28 days between doses)	Baseline PET ²	Day -11	Day 12	Day 22	(7-14 days post-final dose)	Visit may take place on Day -1 or on Day 1 before dosing. Visits will take place at imaging unit; all other visits will take place at clinical units.
Informed consent	X										
Inclusion and exclusion criteria	X										
Demography	X										
Medical history	Х										
Past and current medical conditions	х	X									
Full physical exam including height and weight	x									χ3	Height not required at follow up visit
Brief medical exam		х		Х		X4	х	X ⁴	χ4		 Pre-PET scan, per imaging site SOPs; timing may change in Cohort 2 depending on PET timing.
Pregnancy test	x	x				X ⁵		X ⁵	X ⁵		Pregnancy tests in females, when required, in serum or urine, as per site SOPs. 5. Pre-PET scan; time points may change in Cohort 2 depending on PET timing.
Hepatitis B and Hepatitis C screen	X										
Laboratory assessments (include liver chemistries)	x	х		Χę			X		χ6	x	6. 24 h post-dose
12-lead ECG	х	х	x ⁷	X ⁸			х	χ ⁹	χ ⁸	х	7. 30 min and 2, 4 and 8 h post-dose 8. 24 h post-dose (pre-PET scan in Dosing period 2) 9. Post-PET scan and before leaving imaging unit
Vital signs	x	х	X ⁷	χ8			X	X ⁹	X8	X	Timings may change in Cohort 2. Vital signs include blood pressure, heart rate, respiration rate and temperature.
Oxygen saturation monitoring			Х								Continuous monitoring from pre-dose to 4 h post-dose.
Lung function tests (FEV ₁ ,FVC)	x	х	X ¹⁰	χ11			X			X	10. 1 h post-dose 11. 24 h post-dose

CONFIDENTIAL

204715

	Screening	Dosi	ing per	iod 1	Wash- out		Dos peri	sing od 2		Follow- up	Comments
Procedure	Day ≤-30	Day -11	Day 1	Day 2	(7-28 days between doses)	Baseline PET ²	Day -11	Day 12	Day 22	(7-14 days post-final dose)	Visit may take place on Day -1 or on Day 1 before dosing. Visits will take place at imaging unit; all other visits will take place at clinical units.
DLCO	X	Х		X ¹²							12. 24 h post-dose.
Randomisation			X								
GSK3008348 dosing			Х					X			All post-dose time points are relative to start of nebulisation
PK blood sample			x	х				x	x		In Dosing period 1, pre-dose, and at 15 and 30 min, 1, 2, 4, 8, 12, 18 and 24 h after the start of nebulisation. In Dosing period 2, pre-dose; on Day 1 at 15 and 30 min, 2 and 4 h post-dose; and on Day 2 on arrival and discharge from imaging unit. Time points may change in Cohort 2.
PK urine collection			Х								Spot urine sample to be taken from pre-dose void. Total urine collection from pre-dose to 8 h post-dose.
Biomarker blood sample			х13	X ¹⁴							 Samples at pre-dose, and at 2 and 8 h post-dose. Sample at 24 h post-dose.
PET ligand administration & PET scan						X ¹⁵		X ¹⁶	X ¹⁷		 At least 7 days post-first dose, and no more than 14 days before next PET scan. Approx. 30 min (between 20–60 min) post-dose. Approx. 24 h (between 14–28 h) post-dose. Timing of post-dose PET scans may change in Cohort 2; participants will have a max of 3 PET scans in total.
HRCT						Х					
Immunogenicity blood sample						X ¹⁸				Х	18. Pre-PET scan.
Genetic sample		Х									
AE/SAE & CV event review			Х	Х	X	X	X	X	Х	X	
Concomitant medication review		Х	Х	Х	X	X	X	X	X	X	

ECG: Electrocardiogram, DLCO: Diffusing capacity of the lungs for carbon monoxide, FEV1: Forced expiratory volume in 1 second, FCV: Forced vital capacity, PET: Positron emission tomography, HRCT: High resolution computed tomography, AE: Adverse event, SAE: Serious adverse event, CV: Cardiovascular, PK: Pharmacokinetics

